5.3 Exclusion Criteria

Women who meet any of the following criteria will be excluded from the study:

- 1) Participant report of any of the following at screening or enrollment:
 - a. Previous DAA treatment for HCV (prior interferon-based treatment is acceptable) without documentation of SVR12 (HCV RNA below the lower limit of quantification at least 24 weeks after DAA initiation)
 - Use of any medications contraindicated with concurrent use of velpatasvir or sofosbuvir according to the most current EPCLUSA® package insert³⁰
 - c. Plans to relocate away from the study site area in the next 16 months and unable/unwilling to return for study visits
 - d. History of cirrhosis documented or reported by previous liver biopsy, imaging tests or on at least 2 noninvasive laboratory tests of fibrosis, including compensated cirrhosis
- 2) Reports participating in any other research study involving investigational medications or investigational medical devices within 60 days or less prior to enrollment (does not include research studies involving standard of care medications)
- 3) Known fetal chromosomal abnormality prior to enrollment (confirmed by chorionic villus sampling or amniocentesis)
- 4) Clinically significant and habitual non-therapeutic drug use, not including marijuana, as determined by site Pl/designee at screening and enrollment
- 5) At screening and enrollment, as determined by site PI/designee, any significant, uncontrolled, active or chronic cardiovascular, renal, liver, hematologic, neurologic, gastrointestinal, psychiatric, endocrine, respiratory, immunologic disorder or infectious disease other than HCV (or HIV as outlined in eligibility criteria)
- 6) Any of the following laboratory abnormalities at screening:
 - a. Aspartate aminotransferase (AST) or alanine transaminase (ALT) greater than 10 times the upper limit of normal
 - b. Hemoglobin less than 9 g/dL (90 g/L)
 - c. Platelet count less than 90,000 per mm³ (90,000x10⁹/L)
 - d. International normalized ratio (INR) > 1.5
 - e. Creatinine greater than 1.4 mg/dL (124 μmol/L)
- 7) If living with HIV, CD4 count less than 200 cells/mm³ within 6 months of enrollment.
- 8) Any other condition that, in the opinion of the site PI/designee, would preclude appropriate informed consent, make study participation unsafe, complicate interpretation of study outcome data, or otherwise interfere with achieving study objectives.

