13.2 Study Coordination

This study is a multi-center study with [name] holding the IND at the University of Pittsburgh and the other sites have received an IND exemption from the FDA, their local IRB/REB, or will obtain a Health Canada CTA. Each site will receive IRB/REB approval from their local IRB/REB. Each study site is responsible for understanding and complying with their local and state research guidelines, regulations and laws.

University of Pittsburgh/UPMC Magee-Womens Hospital will provide coordination for the study.

Close coordination between the study teams is necessary to track recruitment, enrollment, retention, AEs and unanticipated problems in a timely manner and to address other issues that may arise. The PSRT will address issues related to study eligibility, AE management/reporting and unanticipated problems as needed to ensure consistency. Rates of accrual, protocol adherence, retention, and AE incidence will be reported by data management and monitored closely by Data Coordinating Center as well as the PSRT.

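### Exclusion 6c gives one platelet threshold as two values that differ 1000-fold: 90,000 per mm³ and, in brackets, 90,000×10⁹/L

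*Protocol*

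**What the plan says.** Protocol section 5.3 opens with the rule "Women who meet any of the following criteria will be excluded from the study". One criterion met is therefore enough to exclude a woman. Item 6 lists the laboratory values at screening that exclude, several of them in two unit systems:

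- 6b: "Hemoglobin less than 9 g/dL (90 g/L"
- 6c: "Platelet count less than 90,000 per mm³ (90,000x10⁹/L"
- 6e: "Creatinine greater than 1.4 mg/dL (124 μmol/L"

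(The closing bracket of each is omitted here.)

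Table 3 in section 7.2 places the blood count with platelets among the local laboratory tests, so the result arrives in whatever unit the local laboratory uses. The protocol does not say which units those are. Section 13.2 says of sites other than the coordinating one that they hold an IND exemption "or will obtain a Health Canada CTA". Sections 8.4.1 and 11.2 also make specific provision for Canada, on safety reporting and on record retention. Section 13 requires all eligibility criteria to be verified before study product is started, and section 12 lists verification of eligibility among the tasks of local monitoring.

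**The concern.** A threshold given in two unit systems should be one threshold. In 6c it is two. A site whose laboratory reports platelets per mm³ reads one limit, and a site whose laboratory reports in multiples of 10⁹/L reads another, 1000 times higher. The bracketed values appear to be there for laboratories of the second kind, and those are the users for whom the printed figure fails.

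What is at stake is the consistency and traceability of an eligibility criterion. Someone checking an SI platelet report against the protocol text would have to conclude that the woman meets an exclusion. If sites instead set the printed SI figure aside, as they probably would, the criterion is applied through a correction that the protocol does not contain.

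**Working it through.** **Inputs.** From section 5.3, item 6: platelets 90,000 per mm³ and 90,000×10⁹/L; hemoglobin 9 g/dL and 90 g/L; creatinine 1.4 mg/dL and 124 μmol/L. From section 5.2, inclusion 5: total bilirubin 3.0 mg/dL and 51 μmol/L. The conversion factors are standard unit arithmetic and are not in the protocol: 1 L = 10⁶ mm³; hemoglobin ×10; creatinine ×88.42; bilirubin ×17.104.

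**Step 1: try to reproduce the bracketed platelet figure.**

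Count per litre = count per mm³ × 10⁶

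90,000 × 10⁶ = 9.0×10¹⁰ per L = 90×10⁹/L

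The printed 90,000×10⁹/L is not reproduced.

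**Step 2: size of the gap.**

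Printed SI figure: 90,000 × 10⁹ = 9.0×10¹³ per L

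Ratio: 9.0×10¹³ / 9.0×10¹⁰ = 1000

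Printed SI figure in the other unit: 9.0×10¹³ / 10⁶ = 90,000,000 per mm³

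**Step 3: do the neighbouring dual-unit values convert?**

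| Test | Conventional | Calculation | Result | Printed | Agrees |
|---|---|---|---|---|---|
| Hemoglobin | 9 g/dL | 9 × 10 | 90 g/L | 90 g/L | yes |
| Creatinine | 1.4 mg/dL | 1.4 × 88.42 | 123.8 μmol/L | 124 μmol/L | yes |
| Total bilirubin | 3.0 mg/dL | 3.0 × 17.104 | 51.3 μmol/L | 51 μmol/L | yes |
| Platelets | 90,000 per mm³ | 90,000 × 10⁶ | 90×10⁹/L | 90,000×10⁹/L | no, 1000-fold |

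Of these four, only the platelet line fails.

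**Step 4: what the printed SI figure would do if applied as written.** The following counts are assumed for illustration and are not from the protocol: 150, 250, 400, 1000 and 5000 ×10⁹/L. All five are below 90,000×10⁹/L, so all five would exclude. None is below 90×10⁹/L, so none would exclude under the converted per-mm³ figure. The literal SI reading therefore leaves no eligible candidate.

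**Step 5: reach.** Section 10.3 builds the sample size from an SVR12 rate of 97% against 92%, a preterm birth rate of 23% with a difference of 13 percentage points, and about 100 participants. The platelet limit enters none of these, nor the tests planned in sections 10.4.2 to 10.4.4.

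**The case against.** **Staff would notice.** The per-mm³ figure stands first on the same line, and a cut-off equal to 90 million per mm³ is plainly impossible to anyone holding a platelet report. An error that excludes everyone shows itself with the first candidate and would not quietly distort who enters. This stands, and it limits the practical harm. It does not make the two figures equal.

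**It may be a character-reading fault.** With an exponent of 6 the line would be consistent, since 90,000×10⁶/L is 90,000 per mm³. This is possible but speculative: the exponent reads cleanly, 10⁹/L is a usual platelet unit, and the neighbouring values in the list are intact. A glance at the protocol page settles it.

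**Controls exist.** Section 13.2 has the safety review team deal with eligibility questions so that sites act consistently, and sections 12 and 13 call for eligibility to be verified. These controls make divergent local readings less likely. But the verification is made against the criteria as written, and none of the controls corrects the text.

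**Stronger readings that the protocol does not support.** A reader might infer that SI-reporting sites would in fact turn away every candidate. That is the literal consequence of the figure, not the likely one. A reader might also infer that an automated REDCap eligibility check carries the wrong number. Sections 10.4.1 and 11.1 describe REDCap as the data capture system, with monitoring and queries, and mention no such check. Finally, the protocol shows that Canadian sites are provided for, but not how many there are or which platelet units they report.

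**Conclusion.** The contradiction is real. Exclusion 6c states a single threshold as two values exactly 1000-fold apart, and nothing else in the protocol says which is meant. The arithmetic rests only on the definition of the litre. The practical weight rests on two things: that some sites may report in SI units, which is an inference from the provision for Canadian sites, and that eligibility is checked against the protocol's criteria, which sections 12 and 13 state.

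This is a wrong figure in a working eligibility criterion. It should be corrected, but it is not a threat to enrollment in practice, and it leaves both primary endpoints, the sample size, the power and the planned comparisons untouched.

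**What to change.** The sponsor should confirm the intended platelet threshold and restate 6c so that each figure is the unit conversion of the other. As a matter of units only, 90,000 per mm³ corresponds to 90×10⁹/L; which clinical limit is intended is for the sponsor to say. As a precaution, look for the same figure in any eligibility worksheets, case report forms or site instructions derived from this line. There is no evidence in the protocol that the error has spread to them.

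The cost is one number, in an amendment or a clarification memo to sites. No analysis or sample size text needs to change.

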6 STUDY MEDICATION

6.1 Regimen

Each participant will take a 12-week course (84 consecutive days) of SOF/VEL(400 mg of sofosbuvir and 100 mg of velpatasvir), one tablet by mouth once daily.

6.2 Administration

Study medication will be dispensed at V2 (Enrollment), V3 and V4 visits. Participants will be given instructions on timing of the dose, what to do if a dose is missed and how to store the medication. If a dose is missed, the participant should take the dose as soon as it is remembered, but only one dose per day (24-hour period). Participants will be instructed to take the medication each day as close to the same time as possible. SOF/VEL can be taken with or without food. Participants will be given adherence tips, such as setting an alarm on their phone, linking medication time to another daily activity, etc. Participants will be instructed to call the study staff immediately if they run out of medication or if they lose the study medication. In this case, all possible efforts will be made to get the participant study medication as soon as possible which may be outside the visits listed above.

6.3 Supply and Accountability

6.3.1 Supply

Gilead Sciences will supply the study medication that is manufactured under Good Manufacturing Practices as FDA approved bulk product. The product will be shipped to each designated site pharmacy location from the drug distributer.

6.3.2 Storage and Dispensing

SOF/VEL should be stored at room temperature below 30°C (86°F).³⁰ The site investigational pharmacist or designee will maintain documentation of temperature in the area where the study medication is stored. Study medications will be dispensed at each site according to the study pharmacy manual and their site SOP for medication provision.

The site pharmacist or designee will dispense enough study medication to last until the next scheduled visit and an additional (emergency/extra) supply. The study medication will be dispensed to the study staff, then subsequently provided directly to the study participant.

6.3.3 Accountability

At each investigational site, the pharmacist or designee will maintain complete accountability records of all study SOF/VEL received and dispensed. Unused

product should be brought back to the study site by participants at each visit and sent to the pharmacy for documentation and quarantine, according to the site SOP. All available unused study medications will be returned to the distributor/Gilead Sciences or destroyed or as instructed by Gilead after the study is completed.

6.3.4 Retrieval of Study Medication

Participants will be instructed to return any unused medication at each visit. If the participant fails to return unused medication at a scheduled visit, reasonable attempts will be made and documented to obtain the unused medication from the participant (i.e. at an unscheduled visit or the following study visit). Unused medication will be accounted for by study staff and documented in the participant's research record and then returned to the site pharmacy for documentation and quarantine, per site SOP or site standards.

6.4 Concomitant Medications

Participants may use non-prohibited concomitant medications during the study. All concomitant medications reported throughout the course of the study will be recorded and will include prescription medications, over-the-counter preparations, vitamins, nutritional supplements, and herbal preparations. Each reported concomitant medication will be reviewed to ensure the participant is not using prohibited medications (i.e. St. John's wort, carbamazepine, efavirenz) as referenced in the EPCLUSA® package insert. At each visit, participants will be asked if they have initiated any new medications or changed any reported medications. If the participant reports using acid suppressing medications, she will be given the option of discontinuing use during the 12-week period of SOF/VEL administration or following specific dosing instructions regarding correct timing of acid suppressing medication use according to the EPCLUSA® package insert.

7 STUDY PROCEDURES

An overview of the study visits and evaluations schedule is presented in Appendix 1. Any clinical or laboratory information collected as a part of the participant's routine clinical care occurring on the same day as the study visit does not need to be repeated and can be collected from the participant's medical record.

7.1 Pre-screening

Sites may perform pre-screening activities as per local standards/local IRB/REB approval. Activities may include:

- Pre-screening medical records for minimum criteria (i.e. age, gestational age, HCV status)
- Use of screening scripts to provide information about the study to individuals who are interested

 Use of IRB/REB approved materials (i.e. ads, flyers, videos, social media posts)

Process information (e.g., number of potential participants contacted, number presumptively eligible) will be recorded and stored at the study site to inform recruitment activities.

Participants will be encouraged to include her partner and/or family members in discussions about study participation as desired.

7.2 Visit 1- Screening (V1)

Potential participants will be encouraged to speak with their primary care/OB provider to determine whether to initiate HCV treatment during pregnancy before enrolling in the study.

Written informed consent will be obtained before any screening procedures are initiated. Screening can take place anytime within the screening gestational age window (12+0 to 29+6 weeks) with gestational age being determined by available clinical information and confirmed by ultrasound prior to enrollment. The screening visit questionnaire will include information about the diagnosis of HCV, any past or ongoing HCV risk factors, and any past HCV care or treatment. If an anatomy ultrasound has not been performed by the time of the screening visit, then it should be performed prior to enrollment as part of routine obstetric care. The study team may assist the participant in scheduling this ultrasound. Multiple visits may be needed to complete all required screening procedures as necessary.

The actual screening visit may occur anytime during the protocol defined screening window of 12+0 to 29+6 weeks. Routine clinical care laboratory values collected up to 4 weeks prior to the **date of the screening visit** may be used for screening purposes. In this case, any STORC screening required laboratory tests that were not done as part of clinical care within 4 weeks should be drawn at the time of the STORC Screening Visit. Any exclusionary laboratory values can be repeated at a later date within the screening window. If the repeated laboratory values meet inclusion criteria, then the participant can be enrolled. If there is concern that the participant's health status has changed between the screening and the enrollment visit or if the study investigators have concerns about the woman's health status, the screening laboratories can be repeated prior to enrollment.

Table 3: Screening Visit (V1)

Table 3: Screening Visit (V1)					
Visit 1- Screening Visit Component Procedures					
Component					
Administrative and Regulatory	 Assess eligibility Review and obtain written informed consent ICF Comprehension Assessment Assign participant ID (PTID) Sign appropriate medical record releases (i.e. to obtain records from prenatal care and outside records as necessary) Collect locator information Collect demographic information Visit questionnaire Provide reimbursement for study visit Schedule next visit 				
Clinical	 Collect medical history & review and print medical/prenatal records including documentation of previous hepatitis C treatment, if applicable Review and obtain documentation of previous liver biopsy, liver imaging and/or noninvasive measures of fibrosis, if applicable Collect concomitant medications Perform full physical examination, including Fetal Heart Tones (FHTs) Confirm gestational dating (by available clinical information but must be confirmed by ultrasound prior to enrollment) 				
Local Laboratory Tests	 Collect blood: Complete blood count (CBC) with differential and platelets* HCV antibody and RNA viral load* HCV genotype (if not available) Hepatic function panel (AST, ALT, albumin, total and direct bilirubin, alkaline phosphatase)* Creatinine/eGFR * If living with HIV, perform HIV RNA PCR (viral load) if not done within 30 days of screening and CD4 cell count if not done within 6 months of screening*** Hepatitis B virus testing (HBsAg, anti-HBc, anti-HBs) if not done as part of routine prenatal care PT/INR* Lipase* Creatine kinase* 				

^{***}If greater than 30 days between screening and enrollment, HIV RNA PCR must be repeated/available and within eligibility criteria to enroll

7.3 Visit 2- Enrollment (V2)

The following procedures will occur at the enrollment visit (V2). The visit questionnaire includes any changes in the participant's medical history and any new or ongoing HCV risk factors. During the enrollment visit the participant will be given instructions on taking the study medication.

^{*}Results of routine clinical care laboratory testing conducted within 4 weeks of screening visit date may be used towards the screening visit.

Table 4: Enrollment (V2)

Enrollment Visit 2 (V2)		
Component Procedures		
Administrative and Regulatory	 Confirm eligibility Review/update locator information Visit Questionnaire Provide counseling regarding protocol adherence Provide reimbursement for study visit Schedule next visit 	
Clinical	 Review/update medical history Review/update concomitant medications Document pre-existing conditions Perform modified physical examination, including FHTs 	
Study Medication	 Provide instructions regarding study medication/daily use Provide study medication and observe first dose (day 1) of medication in office 	
Local Laboratory Tests	 Collect blood: HCV RNA viral load Blood sample for HCV genomic deep sequencing (collected but only used in the case of treatment failure) or stored sample for future use, as applicable If living with HIV and more than 30 days between screening and enrollment, HIV RNA PCR must be repeated prior to enrollment (if a clinical HIV viral load within 30 days of enrollment is not available) 	

7.4 Follow-up Visits

7.4.1 Visit 3 and 4

The following procedures will occur at visits 3 and 4 to assess the safety and tolerability of study medication. The visit questionnaire will assess any changes in the participant's medical history and any new or ongoing HCV risk factors. Participants will also be reminded to call the research staff when they present to the hospital for delivery.

Table 5: Follow-up Visits (V3 and V4)

Follow-up Visits 3 and 4			
Component	ponent Procedures		
Administrative and Regulatory	 Review/update locator information Visit questionnaire Provide modified counseling regarding protocol adherence Provide reimbursement for study visit 		
	Schedule next visit as applicable Review/update medical history		
Clinical	 Review/update concomitant medications Perform modified physical examination, including FHTs Record/update AEs 		
	 Provide available test results (if applicable) Instruction about contacting study staff when in labor/being admitted to labor and delivery 		
Study Medication	 Collect and perform accountability of unused study medication (if applicable) Provide study medication Review instructions for daily use 		

7.4.2 End of Treatment Visit (V5)

The following procedures will occur at the End of Treatment visit. This visit will be scheduled within 7 days of completion of the 12-week course of study medication. The purpose of this visit will be to collect any remaining study medication and to assess and follow-up on any adverse events. The visit questionnaire will assess any changes in the participant's medical history and any new or ongoing HCV risk factors. Participants will also be reminded to call the research staff when they present to the hospital for delivery.

Table 6: End of Treatment Visit

End of Treatment Visit		
Component Procedures		
Administrative and Regulatory	 Review/update locator information Visit Questionnaire Protocol adherence counseling, including delivery visit instructions Provide reimbursement 	
Clinical	 Review/update medical history Review/update concomitant medications Perform modified physical examination, including FHTs Record/update AEs Provide available test results (if applicable) 	
Study Medication	Collect and perform accountability of remaining study medication	
Local Laboratory Tests	 Collect blood for: HCV RNA viral load Blood sample for HCV genomic deep sequencing (collected but only used in the case of treatment failure) or stored sample for future use, as applicable 	

7.4.3 Delivery Visit (in person or phone visit and chart review)

Participants will be instructed to contact the study staff when they are in labor/admitted to labor and delivery, regardless of delivery location; a family member or friend may provide this information to study staff. If the participant has not yet completed study medication, she will be instructed to bring the remaining medication with her to the hospital to continue daily dosing and avoid missed doses. If necessary and possible, additional doses may be dispensed during admission if the participant did not bring study medication with her and is unable to access it.

The delivery visit may occur in person, for participants who are delivering at the hospital associated with the study site. For participants who are delivering at a non-

associated clinic or at a time in which the study staff is unable to provide an in person visit, the visit may be conducted utilizing information contained in the delivery medical records and/or by participant report. The date of this delivery visit will be the date the study staff makes the first contact with the participant during her delivery admission, regardless if procedures occur over more than one day. Participants who deliver at an outside location will be contacted by phone as close to delivery as possible to complete the applicable delivery visit study procedures (i.e. questionnaire, update locator information, update medical history). The delivery visit date for these participants will be the date of the completed phone call. Available medical records to obtain delivery outcomes/variables will be reviewed for all participants, regardless of delivery location. A copy of the delivery records will be placed in the participant's research chart. In the event that the participant delivers at the hospital associated with the clinical site and is still taking study medication, then procedures from previously scheduled visits (V3 or V4) can be performed. Regardless of location of delivery, participants who are still on study medication at

the time of delivery will be encouraged to continue on the medication to complete the full 12-week course (84 doses) of study medication.

Table 7: Delivery Visit

Delivery Visit Delivery Visit		
Component	Procedures	
Administrative and Regulatory	 Review/update locator information Visit Questionnaire Protocol adherence counseling (for mother and infant) Provide reimbursement, as applicable Schedule next visit 	
Clinical (Maternal)	 Review/update medical history Review/update concomitant medications Provide available test results (if applicable) Perform modified physical examination (or obtain from medical record) Record/update AEs 	
Study Medication	 Study medication use/adherence (if still on study medication) Dispense study medication, as applicable, to complete 12-week course (if still on study medication) 	
Clinical (Infant)	 Record concomitant medications Full physical examination (may be done via chart review) 	
Medical Record Review for Delivery Outcomes	 Type of pregnancy outcome Gestational age at pregnancy outcome If delivery, type of delivery (e.g., vaginal, vaginal forceps-assisted, vaginal vacuum-assisted, cesarean section) Delivery medications Complications related to pregnancy outcome Delivery complications (e.g., intrapartum and/or postpartum hemorrhage, hypertension, admission to the neonatal ICU) Other complications not related to delivery 	
Baseline Infant Information*	 Demographics Sex Weight Length Head circumference Apgar scores 	
Local Laboratory Test**	Collect blood: Maternal HCV RNA viral load	

^{*}All baseline infant information may be extracted from the infant medical record as available.

